9.4 STATISTICAL ANALYSES

A statistical analysis plan (SAP) will be written for the study that contains detailed descriptions of the analyses to be performed. The SAP will be finalized prior to the database lock and unblinding of the data. The approach to analyses affected by the COVID-19 or other pandemic crisis will be described in the SAP along with the analyses for the exploratory objective.

9.4.1 GENERAL APPROACH

The design of this randomized controlled study is a placebo-controlled investigation of the combination of NMES and ECC vs NMES placebo + ECC placebo. Continuous variables will be summarized using descriptive statistics including n, mean, median, standard deviation, range (e.g., minimum and maximum). Qualitative variables will be summarized using counts and percentages. Summaries will be provided by treatment group and overall. Unless otherwise specified, statistical analyses will be performed using SAS Version 9 or higher. For the co-primary endpoints, the nominal significance level is 0.025 (two-sided test with a Bonferroni adjustment for two comparisons); for all other statistical tests, the nominal significance level is 0.05 (two-sided). p-values and confidence intervals will be reported.

Linear models will be used for most analyses (primary and key secondary endpoints that are

continuous), with terms for treatment group, type of graft, surgeon, age, gender and baseline in all models.

9.4.2 ANALYSIS OF THE PRIMARY EFFICACY ENDPOINTS

The primary hypotheses will be tested at the two-sided 0.025 level, adjusting for the multiple comparisons of 2 co-primary endpoints. Separate linear models will be fit for each of the two co-primary endpoints, one for the 9-month and one for the 18-month changes from baseline in isokinetic quadriceps muscle strength. As described above, the model will include treatment group, type of graft, surgeon, age, gender, and baseline isokinetic quadriceps strength symmetry index. Least-squares (LS) mean change from baseline, along with associated standard errors, will be presented for each intervention group. For the comparisons of combination NMES + ECC to the placebo group, group LS mean differences in the change from baseline will be presented, along with associated 97.5% upper confidence bounds and p-values. The primary analysis of the primary endpoints will use the mITT analysis set. A secondary analysis of the primary endpoints will use the PP analysis set. Appropriate non-linear parametric or non-parametric tests may be applied if the assumptions of the model are not satisfied. Details will be presented in the SAP.

Assessment of the extent of missing data and its mechanism will be explored for the primary endpoints using the mITT analysis set. Graphical and numerical descriptive methods will be used to summarize and the primary outcome over time by intervention group and overall. We will begin by assuming missing at random, and employ multiple imputation methods^{45,46} to handle missing data. Other more complicated methods may be employed if there are concerns about differential follow-up and nonignorable missing (where the stochastic process that generates missingness is explicitly modeled such as a pattern mixture model⁴⁷) as a sensitivity analysis. The model will include the same covariates that are included in the primary analysis.

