9 STATISTICAL CONSIDERATIONS

9.1 STATISTICAL HYPOTHESES

The primary hypothesis is that quadriceps strength symmetry will be greater with the combination of NMES and ECC relative to the placebos at both 9 months and 18 months post-ACLR. Statistically, the following null and alternative hypotheses will test the superiority of the combination of NMES + ECC versus placebo arm in the change from baseline to 9 months and 18 months post-ACLR in isokinetic quadriceps strength symmetry index separate analyses:

$$\begin{aligned} H_01: \Delta_{9\text{mo}} \text{ NMES + ECC} &\leq \Delta_{9\text{mo}} \text{ NMES placebo + ECC placebo} \\ H_{A1}: \Delta_{9\text{mo}} \text{ NMES + ECC} &> \Delta_{9\text{mo}} \text{ NMES placebo + ECC placebo} \\ H_{06}: \Delta_{18\text{mo}} \text{ NMES + ECC} &\leq \Delta_{18\text{mo}} \text{ NMES placebo + ECC placebo} \\ H_{A6}: \Delta_{18\text{mo}} \text{ NMES + ECC} &> \Delta_{18\text{mo}} \text{ NMES placebo + ECC placebo} \end{aligned}$$

where Δ reflects the adjusted mean change from baseline at 9 or 18 months post-ACLR in isokinetic quadriceps strength symmetry index.

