9.2 SAMPLE SIZE DETERMINATION

For the main study objectives, the sample size of 112 participants (56 per each of the 2 treatment groups) allows sufficient power to test the primary hypotheses regarding two separate comparisons (each co-primary endpoint) of the combination NMES + ECC vs NMES placebo + ECC placebo. Each test will be conducted using a two-sided 0.025 Type I error level ($=0.05/2$, the Bonferroni adjustment for two comparisons). We hypothesize that the effect size (treatment difference / standard deviation) will be at least 0.7 for the tests of NMES + ECC vs NMES placebo + ECC placebo. Assuming 20% drop-out (resulting in an effective sample size of 45 per group), we have at least 80% power to detect this effect size. Preliminary data from the

same site with a comparable patient population and primary endpoint demonstrated a 1.14 effect size. Because of the small sample size and variability in measurements in this preliminary study, we conservatively reduced the effect size for this study.³⁵

An additional cohort of 28 participants will be studied – the SOC control group. The sample size of 28 participants for this group is based on feasibility considerations.

Thus, the total sample size for the trial is 140 participants.

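### Fixed Bonferroni at 0.025 for the two primary endpoints is valid but leaves power unused; Holm rejects everything it rejects within the same family-wise 0.05.

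*Combined protocol and SAP*

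**What the plan says.** Section 9.1 sets out one null and alternative pair for the change to 9 months and another for the change to 18 months, to be tested "in isokinetic quadriceps strength symmetry index separate analyses". Superiority means a larger change with NMES + ECC than with placebo.

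Section 9.2 sizes the trial "regarding two separate comparisons (each co-primary endpoint") and adds: "Each test will be conducted using a two-sided 0.025 Type I error level", which it derives as 0.05/2. It assumes that "the effect size (treatment difference / standard deviation) will be at least 0.7" and, with 45 per group left after 20% drop-out, concludes that "we have at least 80% power to detect this effect size".

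Section 9.4.1 repeats that for these endpoints "the nominal significance level is 0.025 (two-sided test with a Bonferroni adjustment for two comparisons"), and Section 9.4.2 says the same: "The primary hypotheses will be tested at the two-sided 0.025 level, adjusting for the multiple comparisons of 2 co-primary endpoints". Group differences are to be reported "along with associated 97.5% upper confidence bounds and p-values".

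No section gives a step-down, fixed-sequence or alpha-recycling rule. None says outright whether success needs one endpoint or both.

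**The concern.** The two hypotheses are tested separately and 0.05 is split between them. The natural reading is that either time point may be claimed alone, with the chance of any false claim held at 0.05. Fixed Bonferroni meets that aim but is stricter than it requires. Once one endpoint is rejected at 0.025, the other can be tested at 0.05 without the family-wise error exceeding 0.05.

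Take p = 0.01 at 9 months and p = 0.035 at 18 months. The plan would establish only the 9-month benefit; Holm would establish both. What is at stake is the second claim, often the longer-term one. The validity of the test is not in question.

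The reporting statement raises a related problem. If the difference is NMES + ECC minus placebo, superiority is shown by a lower limit above zero, and an upper bound gives no information on that.

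**Working it through.** **Inputs.** Two-sided 0.025 per test, effect size 0.7, 56 randomized per arm, 20% drop-out and pilot effect 1.14 (all Section 9.2). *Assumed:* two-sample t tests without covariates or imputation, the same effect at both times unless stated, and correlation 0 to 0.9 between the two test statistics.

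**1. The plan's figure.** Effective n = 56 × 0.8 = 44.8, taken as 45. Noncentrality = 0.7 × √(45/2) = 3.320, with 88 degrees of freedom. The critical value at two-sided 0.025 is 2.280, giving power of 84.9% (86.0% by normal approximation). The claim of at least 80% per endpoint holds. At two-sided 0.05 the critical value is 1.987 and power is 90.7%.

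**2. Why Holm stays within 0.05.** Holm compares the smaller p-value with 0.025 and, only if that is significant, the larger with 0.05.
- Both nulls true: any false claim needs at least one p ≤ 0.025, so its probability is at most 2 × 0.025 = 0.05.
- One null true: a false claim needs that endpoint's p ≤ 0.05, so its probability is at most 0.05.

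Neither step uses the correlation. Every endpoint with p ≤ 0.025 is still rejected.

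**3. Threshold for the second endpoint.** In standardized units, 2.280 × √(2/45) = 0.481 under the plan and 1.987 × √(2/45) = 0.419 under Holm.

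**4. Power at effect size 0.7, 45 per arm** (2,000,000 simulated pairs of correlated t statistics per correlation). At least one = 2 × 84.9 − both under the plan. Holm per endpoint = 84.9 + half the gain in both.

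| Correlation | 0 | 0.5 | 0.7 | 0.9 |
|---|---|---|---|---|
| Both, plan (%) | 72.1 | 75.5 | 77.6 | 80.7 |
| Both, Holm (%) | 82.0 | 83.7 | 84.8 | 86.3 |
| Per endpoint, plan (%) | 84.9 | 84.9 | 84.9 | 84.9 |
| Per endpoint, Holm (%) | 89.8 | 89.0 | 88.5 | 87.7 |
| At least one, either rule (%) | 97.7 | 94.3 | 92.2 | 89.1 |

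**5. Other effect sizes, range over the correlations.**

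| Effect size | Per endpoint, plan → Holm (%) | Both, plan → Holm (%) |
|---|---|---|
| 0.6 | 71.4 → 75.3-77.8 | 51-65 → 64-73 |
| 0.8 | 93.3 → 94.9-96.2 | 87-91 → 93-94 |
| 0.9 | 97.5 → 98.3-98.8 | 95-97 → 98 |
| 1.14 | 99.9 → 99.9 | no material gain |

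- Better early retention (assumed 53 per arm at 9 months, 45 at 18 months, effect 0.7): 90.6% → 92.2-94.1% at 9 months and 84.9% → 89.2-90.3% at 18 months.
- Weaker late effect (assumed 0.7 at 9 months and 0.5 at 18 months, normal approximation): 18-month power 55.2% → about 64-66%.

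**6. Actual family-wise error.**
- Both nulls true, correlation 0 / 0.5 / 0.7 / 0.9: 0.049 / 0.047 / 0.043 / 0.036, identical under both rules.
- One null true: 0.025 under the plan. Under Holm, 0.038-0.047 if the other effect is 0.7 (normal approximation) and 0.050 if it is 1.14.

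**7. The confidence bound.** At an observed standardized difference of 0.7, the two-sided 97.5% interval is 0.7 ± 0.481, or 0.219 to 1.181; its lower limit shows superiority. A one-sided 97.5% upper bound is 0.7 + 0.419 = 1.119. Such a bound lies above zero 97.5% of the time when there is no effect at all. A one-sided 97.5% bound also uses 1.987, the two-sided 0.05 critical value, so even a lower bound of this kind would disagree with the 0.025 test for observed differences between 0.419 and 0.481.

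**The case against.** The strongest reply is that nothing is broken. Three sections agree on 0.025, the stated power is met, and Bonferroni is a legitimate choice. That is accepted, and it is why this is only an optional improvement.

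The extra power has a price. With exactly one true null, the false-claim rate rises from 0.025 to as much as 0.05. With both nulls true and correlation 0.7, the chance of two false claims rises from 0.7% to 1.4%. Both facts stand and should be stated, but they remain within the 0.05 bound that the plan sets.

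Bonferroni also gives 97.5% intervals that always agree with the tests. Under Holm, an endpoint rejected only at the second step can have a 97.5% interval that includes zero. This is a real loss.

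The gain may be smaller than at the planning values. Section 5.5 reports 100% pilot retention and 95% agreeing to return at one year. If those rates held (assumed 56 per arm at 9 months and 53 at 18 months, effect 0.7), the plan would already give 92.2% and 90.6%, and Holm would add about 2 to 4 points per endpoint.

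Finally, that each time point can be claimed alone is an inference. Section 9.1 words the primary hypothesis as benefit at both times. If both were required, each could be tested at 0.05 with no adjustment, and power for both would be 83.4-88.5% by normal approximation. The Bonferroni split makes sense only if either may succeed alone, but the plan should state the rule.

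**Conclusion.** The point holds as an efficiency gain; the planned test is not invalid. At the planned minimum effect of 0.7 with 45 per arm, Holm adds about 3 to 5 points of power per endpoint and about 6 to 10 points for showing benefit at both times. It adds nothing to the chance of at least one significant endpoint. The gain is larger if the effect falls short of 0.7, is 1 to 3 points per endpoint at 0.8, and is immaterial at 1.14. Error control within 0.05 needs no assumption about correlation; the power figures rest on the assumptions listed in the working.

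The reporting of upper confidence bounds is wrong as written and needs correcting whichever multiplicity rule is kept.

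**What to change.** Before the SAP is final and the data are unblinded, replace fixed Bonferroni in Sections 9.2, 9.4.1 and 9.4.2 with:

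> The two primary endpoints will be tested by the Holm procedure at a two-sided family-wise level of 0.05. The smaller p-value is compared with 0.025; if significant, the larger is compared with 0.05. Benefit may be claimed at each time point whose null hypothesis is rejected in favor of NMES + ECC.

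In Section 9.2, state explicitly that the 80% power is per endpoint. In Section 9.4.2, replace the upper bounds with two-sided 97.5% confidence intervals for the LS mean difference. If Holm is adopted, note that these may not match an endpoint rejected only at the second step.

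The cost is a protocol amendment, which the Statement of Compliance makes subject to IRB approval. Because the DSMB reviews efficacy by arm (Section 10.1.6), the record should show that the change was made by staff who had not seen results by arm. Enrolment, visits and data collection are unaffected. If the team prefers intervals that always agree with the tests, keeping Bonferroni is defensible, and only the confidence-bound correction is then needed.

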4 STUDY DESIGN

4.1 OVERALL DESIGN

In order to determine whether high intensity NMES +ECC can improve quadriceps strength better than the current standard of care (NMES placebo + ECC placebo) (primary objective), we propose a comparative effectiveness, single-center, randomized, double-blind, parallel group, placebo-controlled trial of NMES and ECC in patients with ACLR. One-hundred twelve participants scheduled to undergo an ACLR will be randomized into one of two study arms: 1) NMES + ECC ; or 2) NMES placebo + ECC placebo. All participants regardless of assignment will undergo standard of care ACL rehabilitation that focuses on minimizing effusion, restoring range of motion, and improving muscle strength (standard concentric exercises). The study intervention duration is 14-18 weeks, with NMES and NMES placebo beginning within 2 weeks of the ACLR and is provided twice/week for 8 weeks and ECC and ECC placebo beginning 6-10 weeks post-ACL surgery and is provided twice/week for 8 weeks.

Additionally, 28 patients will be enrolled into a control group where no study interventions are provided and participants will be followed and tested as they undergo physical therapy as prescribed by their treating physician. These patients are eligible for the study but refuse to participate in the randomized controlled trial however, they are willing to participate in the study procedures to provide efficacy measures.

We will randomize participants to treatment groups using minimization, a method of unbiased allocation ensuring balance across stratification factors: meniscal injury and treatment, articular cartilage injury (described below), sex and graft type. (See section 6. 3 for details on the randomization method using the minimization method.)

Our primary outcomes will be examined at three study time points: 1) pre-ACLR (within 2 weeks prior), 2) 9 months post-ACLR (± 2 weeks), and 3) 18 months post-ACLR (± 2 weeks). MRI and X-ray measures will be collected at 18 months post-ACLR, biomechanical measures at 9 and 18 months post-ACLR, hop testing at 9 and 18 months post-ACLR and questionnaires at all 3 time points. Additionally, we will examine change in quadriceps muscle strength and muscle volume from baseline to post-NMES intervention (testing visit 2) and post-ECC intervention (testing visit 3) in an attempt to understand the effects of the individual components of the combined NMES+ECC intervention.

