6.2 MEASURES TO MINIMIZE BIAS: RANDOMIZATION AND BLINDING

Procedures for assignment to a study group: Participants in the treatment groups will be allocated to one of the two study arms using minimization^{38,39}, a method of unbiased allocation ensuring balance across confounding factors. This approach is selected over the more common random permuted blocks within stratum design because of the importance of controlling for two known confounders (1) meniscal injury and treatment and (2) articular cartilage injury – that have $4 \times 3 = 12$ combinations. Some of these combinations are relatively rare (e. g. meniscal tear left intact) which would result in potential imbalance (and subsequent loss of power) among the study arms. We will also include graft type (bone-patellar tendon-bone or quadriceps tendon, hamstring,) and sex as minimization factors. A secure web-based application developed by the Data Coordinating Center will be used by the research coordinator to enter participant information (e. g. , participant ID, minimization factors) and to obtain the assigned study arm.

The following definitions of meniscal tears/treatment will be used for minimization: 1) normal/intact; 2) torn/excision (partial or complete); 3) torn/repaired; 4) torn/left intact. Articular cartilage injury will be defined using the Modified Outerbridge Scale and used in minimization as follows: 1) grade 1 (normal or soft); 2) grade 2 (partial thickness lesions); and 3) grade 3 and 4 (full-thickness lesions).

Blinding. Considerable care will be taken to ensure fidelity of blinding. Study staff will have standardized scripts to describe treatment arms to participants in order to prevent different treatment expectations. Study staff collecting outcome measures will not be aware of treatment assignment. Physical therapists, delivering the interventions, will be provided with treatment allocation from the DCC. Blinded data reviews will be done and the statistical analysis plan will be written prior to database lock and unblinding of statisticians.

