9.4.7 SUB-GROUP ANALYSES

Age at time of ACLR and BMI are other biological factors that can influence ACLR outcomes and thus will be considered as covariates and adjusted for in our analyses, as described above. Evaluation of model diagnostics will be included to avoid over-fitting because of the number of parameters that are being assessed.

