9.4.9 EXPLORATORY ANALYSES

Several planned exploratory analyses will be conducted:

- For the primary endpoints, we will incorporate articular cartilage injury and meniscus injury and treatment as covariates in the linear model, with attention to fit statistics to avoid over-fitting.
- For endpoints used to assess the secondary objective 1 (i.e. , T1 relaxation ratio at 18 months post-ACL and T2 relaxation ratio at 18 months post-ACL), we will also explore activity during the return to activity period, activity level prior to injury, BMI and other interaction effects to assess effect modification, with caution to avoid over-fitting
- We will also examine the ability of quadriceps strength at 9 months post-ACLR to predict changes in cartilage health at 18 months post-ACLR. To do this we will employ linear models with several parameterizations of strength (e. g. , continuous, quartiles, binary threshold), assessing the discrimination and calibration for the prognostic models (will include other potential factors in addition to 9-month post-ACLR strength). Additional relationships among variables, such as the correlation of T2 and T1rho MRI measures of OA to X-ray measure of OA, will be explored graphically, summarized descriptively, and modeled using multivariable linear or logistic models.
- We will examine change in quadriceps muscle strength and muscle volume from baseline to post-NMES intervention (testing visit 2) and post-ECC intervention (testing visit 3) in an attempt to understand the effects of the individual components of the combined NMES+ECC intervention.

Several exploratory analyses will be performed to assess the ability to reduce the NMES and

ECC intensity in the placebo treatment group so that it reflects a “true” placebo condition. The SOC control group is a group of participants who were eligible for the randomized controlled trial but refused and were willing to consent to an observational arm.

Specifically,

- The demographic and baseline variables will be summarized in the SOC control group (no NMES or ECC treatment) using equivalent tabular and graphical methods to those described in Section 9.4.5.
- The co-primary and key secondary endpoints will be summarized in the SOC control group for all observed cases.

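### The primary model leaves out two of the four minimisation factors, and so gives up some power if meniscal and cartilage injury predict strength symmetry

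*Combined protocol and SAP*

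**What the plan says.** Section 4.1 describes minimisation as "ensuring balance across stratification factors: meniscal injury and treatment, articular cartilage injury (described below), sex and graft type". Section 6.2 prefers it to permuted blocks "because of the importance of controlling for two known confounders (1) meniscal injury and treatment and (2) articular cartilage injury". With 4 × 3 = 12 combinations, some of them rare, section 6.2 says blocking could leave sparse cells "which would result in potential imbalance (and subsequent loss of power) among the study arms".

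Section 9.4.1 specifies linear models "with terms for treatment group, type of graft, surgeon, age, gender and baseline in all models", and section 9.4.2 repeats the list for both co-primary endpoints: "As described above, the model will include treatment group, type of graft, surgeon, age, gender, and baseline isokinetic quadriceps strength symmetry index". Neither list has a meniscal or cartilage term.

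The two factors appear elsewhere. Section 9.4.9 plans, for the primary endpoints and as exploratory work, to "incorporate articular cartilage injury and meniscus injury and treatment as covariates in the linear model, with attention to fit statistics to avoid over-fitting". Section 9.4.3 puts both into the models for the T1 and T2 ratios at 18 months. Section 9.4.7, on age and BMI as covariates, adds a caution: "Evaluation of model diagnostics will be included to avoid over-fitting because of the number of parameters that are being assessed".

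On missing outcomes, section 9.4.2 says: "We will begin by assuming missing at random, and employ multiple imputation methods". A later sentence says the model will use the primary analysis's covariates. It follows the pattern-mixture text, so it is unclear whether it also governs the imputation model.

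**The concern.** Minimising on a prognostic factor makes the arms more alike on it than simple randomisation would, so the treatment estimate varies less. A model that omits the factor does not register this: the factor's variance stays in the residual, the model standard error is too large, and the test rejects too rarely under the null. Part of the precision that minimisation was chosen to protect is then not used.

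This is a matter of efficiency only. The error is in the conservative direction, and what is at stake is a few points of power on each co-primary test. The exploratory model in section 9.4.9 does not recover them, because it does not change the confirmatory test.

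**Working it through.** **Inputs from section 9.2.** Two-sided α = 0.025 per co-primary endpoint; effect size d = 0.7; 112 randomised, 56 per arm; 20% drop-out, so 56 × 0.8 = 44.8, taken as 45 per arm; power stated as at least 80%.

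**The plan's own figure.** Power = Φ(d√(n/2) − z), with z = 2.241 for α = 0.025. Here 0.7 × √22.5 = 3.320, and Φ(3.320 − 2.241) = Φ(1.079) = 0.860. The noncentral t gives 0.849. The stated figure is reproduced.

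**Approximation under perfect balance.** Let R² be the share of the planned model's residual variance that the two factors explain. The documents give no value, so a range is used. Then:

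- planned type I error = 2[1 − Φ(z/√(1−R²))]
- planned power = Φ((d√(n/2) − z)/√(1−R²))
- power with the factors added = Φ(d√(n/2)/√(1−R²) − z)

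At R² = 10%, √0.9 = 0.949. This gives type I error 2[1 − Φ(2.363)] = 0.0181, planned power Φ(1.137) = 0.872, and adjusted power Φ(3.500 − 2.241) = 0.896.

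| R² | Planned type I error | Planned power | Power with both factors |
|---|---|---|---|
| 0 | 0.0250 | 86.0% | 86.0% |
| 5% | 0.0215 | 86.6% | 87.8% |
| 10% | 0.0181 | 87.2% | 89.6% |
| 20% | 0.0122 | 88.6% | 92.9% |

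These figures ignore imperfect balance and the degrees of freedom spent on covariates, so simulation is needed for realistic levels.

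**Simulation with the planned multiple imputation.** 112 patients were minimised on the four factors and 22 outcomes were missing at random, leaving 90. Assumptions, none of them in the documents:

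- meniscus 40/20/30/10% with cartilage 60/25/15%, or meniscus 55/15/25/5% with cartilage 80/12/8%
- an 80% biased coin, or deterministic assignment
- two graft levels 60/40, sex 50/50, four equal surgeons
- R² shared equally by the two factors
- d in units of the planned model's residual SD

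There were 20,000 replicates per setting and 20 imputations, combined by Rubin's rules. Monte Carlo SE is about 0.3 power points and 0.0011 for type I error. Ranges span the four combinations of prevalence set and assignment rule.

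| R² | Planned power | Change, torn/left-intact level pooled | Change, unpooled |
|---|---|---|---|
| 0 | 80.8–81.5% | −0.8 to −1.1 | −1.0 to −1.8 |
| 5% | – | +0.3 to +0.7 | +0.1 to +0.7 |
| 10% | 81.6–82.1% | +1.9 to +2.2 | +1.9 to +2.6 |
| 20% | 82.3–82.9% | +5.1 to +5.4 | +5.4 to +5.9 |

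Type I error of the planned test is 0.018–0.021 at R² 10% and 0.015–0.018 at 20%. With both factors added it is 0.024–0.026 pooled and 0.022–0.025 unpooled. Break-even R² is about 3.0–4.0% pooled and 3.2–4.9% unpooled. If the factors are in the analysis model but not in the imputation model, the unpooled gain falls to 0.9–1.4 points at R² 10% and 2.6–2.9 at 20%, about half.

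**Cross-check.** A separate complete-case simulation (16,000 replicates, meniscus 40/25/28/7%, unequal surgeon shares, deterministic assignment, unpooled) gave planned type I error of 0.0247, 0.0226, 0.0202 and 0.0154 at R² 0, 5%, 10% and 20%. Power moved from 82.1 to 81.2%, 82.8 to 83.4%, 83.0 to 85.5%, and 83.6 to 89.5%. With each patient assigned by a fair coin, the planned model's type I error was 0.0255–0.0275 across R² 0 to 30%. The conservatism therefore comes from balancing on factors that the model omits.

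**Model size.** With four surgeons, the planned model has 9 parameters and 90 − 9 = 81 residual degrees of freedom. Adding 3 meniscal and 2 cartilage terms gives 14 and 76; with one meniscal level pooled, 13 and 77. The torn/left-intact level had a median of 9 (at 10% prevalence) or 4 (at 5%) of the 90 observed. It was empty in one arm in about 1% or 11–14% of trials.

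**The case against.** The best defence is that the choice looks deliberate. Section 9.4.3 adds exactly these two factors to the cartilage models, and section 9.4.9 keeps them exploratory for strength. Section 6.2 does not name the outcome for which they are confounders, so that passage is weaker evidence that they predict strength symmetry. This stands as context. However, section 9.4.3 gives no reason to leave them out of the strength model, and it shows that a model of similar size is acceptable. That also weakens the over-fitting argument.

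Second, the sign of the benefit cannot be settled from the documents. Below an R² of about 3–5% the change loses power, and at R² 0 it is the option that can slip just under 80%. This stands in full, and it keeps the point to a recommendation.

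Third, the gain depends on what 0.7 is a multiple of. Suppose it refers to the unadjusted SD and the listed covariates explain 20–30% of the variance (an assumption). In a complete-case run of 8,000 replicates, planned power was then about 90–94% and the gain at R² 10% about 1.0–1.5 points. A true effect above 0.7 would shrink it further; section 9.2 calls 0.7 a conservative reduction from 1.14.

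Fourth, two inputs are simplified. The synopsis (1.1) describes 122 randomised with 10 removed from analysis, and section 5.5 also mentions the 10; the simulations minimise exactly 112. Section 9.4.7 says BMI will be adjusted for, which would take one more degree of freedom from each model. Neither affects the direction.

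Finally, both models would be run in either case. But which one is primary decides the confirmatory test, so exchanging them is a real change.

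**Conclusion.** The point holds as an efficiency improvement. It is not an error in any stated figure, and the planned analysis is valid without it: the power claim in section 9.2 survives in every setting run. Under minimisation the planned test is at or below its nominal level, within simulation error, and more conservative the more prognostic the omitted factors are.

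The gain is negligible at a partial R² of 5%, about 2 points at 10% and about 5 to 6 at 20%, against a loss of 1 to 2 points if the factors are not prognostic. These sizes rest on assumed R², prevalences, surgeon numbers and assignment rule. Confidence is therefore medium: the omission and the direction are certain, but the size is not. If the sponsor believes that meniscal and cartilage injury do not predict strength symmetry, saying so in the plan would be an adequate answer.

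**What to change.** Before unblinding, amend section 9.4.2, with section 9.4.1 to match, and carry the change into the SAP:

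1. Add meniscal injury and treatment, and articular cartilage injury, to the linear model for both co-primary endpoints, coded as for minimisation.
2. Pre-specify a blinded rule for sparse levels such as torn/left intact: a minimum overall count, and the level into which a smaller one is merged. This also answers the over-fitting caution.
3. List the covariates of the multiple-imputation model and include both factors. That list is needed in any case.
4. Keep the present model as a sensitivity analysis. The first exploratory item in section 9.4.9 then becomes redundant.

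The cost is a protocol amendment, which needs IRB approval before implementation (Statement of Compliance), and matching SAP text, which section 9.4 has finalised before database lock and unblinding. No new data are needed, because both factors are already entered to obtain the allocation. If the factors prove not to be prognostic, power would be 79.9–80.3% with pooling or 79.0–80.2% without, against 80.8–81.5% for the current model.
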